Official Title: The Impact of Stationary Combined Exercise on Adiponectin and High-Sensitivity C-Reactive Protein Levels in Overweight Women

NCT Number: NCT number pending

Document Type: Study Protocol with Statistical Analysis Plan

Document Date: January 15, 2024

Sponsor/Institution: College of Physical Education and Health, Chongqing College of International Business and Economics, Hechuan, Chongqing, China

Study Protocol Overview

This document describes the full study protocol and statistical analysis plan for the research titled "The Impact of Stationary Combined Exercise on Adiponectin and High-Sensitivity C-Reactive Protein Levels in Overweight Women." The study was approved by the Research Ethics Committee of Chongqing College of International Business and Economics (Approval No. K2016038) on January 15, 2024. It was conducted between January 20, 2024, and April 10, 2024, with 22 overweight female participants randomly assigned to either an exercise or a control group. The exercise intervention consisted of an eight-week circuit-based combined training program performed four times per week at 70–90% of maximum heart rate. Measurements included serum adiponectin and hs-CRP concentrations (ELISA), as well as body composition and VO_{max} assessments at baseline and 48 hours post-intervention. Statistical analysis included paired t-tests for within-group changes, ANCOVA for between-group comparisons, and Pearson correlation for associations between biomarkers. Significance was determined at $P < 0.05$ using SPSS version 17.

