# 4. General Analysis Principles

All tests two-sided with  $\alpha = 0.05$ . Continuous variables summarized by mean $\pm$ SD (or median [IQR] if non-normal); categorical variables by counts and percentages. Assumptions checked by Shapiro-Wilk (normality) and Levene's test (homogeneity of variance). When assumptions are violated, appropriate transformations (e.g., log for hs-CRP) or non-parametric methods are used.

Effect sizes and precision will be reported: adjusted mean differences with 95% confidence intervals (CI) from ANCOVA; within-group standardized mean changes (Cohen's d); and partial  $\eta^2$  for ANCOVA.

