## 6. Multiplicity Control

Two primary endpoints (adiponectin and hs-CRP) will control family-wise error at 0.05 using Holm–Bonferroni adjustment. Secondary outcomes are exploratory; nominal p-values will be reported with 95% CIs.

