## **13. Sample Size Considerations**

A total sample of 22 participants (11 per arm) was planned based on feasibility. No formal power calculation was performed; the study is powered for detecting moderate-to-large effects and intended as hypothesis-generating with controlled Type I error through multiplicity adjustment for co-primary endpoints.

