## **16. Data Presentation Standards**

Report means with one decimal where appropriate; hs-CRP to two decimals; exact p-values to three decimals (e.g., p=0.047). Confidence intervals at 95% two-sided. Units consistent with laboratory reports (adiponectin  $\mu\text{g/mL}$ ; hs-CRP  $\text{mg/dL}$ ).

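### Does the protocol's plain P < 0.05 undercut the Holm adjustment that the SAP sets for the two primary endpoints?

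*Protocol*

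**What the plan says.** The protocol overview lists the methods in one sentence, "Statistical analysis included paired t-tests for within-group changes, ANCOVA for between-group comparisons, and Pearson correlation for associations between biomarkers", and follows it with "Significance was determined at $P < 0.05$ using SPSS version 17". It names no multiplicity procedure and does not separate primary from other tests.

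The SAP has more detail:

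- Section 4 gives a general default: "All tests two-sided with" α = 0.05. It also asks for "adjusted mean differences with 95% confidence intervals (CI) from ANCOVA".
- Section 6 states that the two primary endpoints "will control family-wise error at 0.05 using Holm–Bonferroni adjustment". For the rest it says "Secondary outcomes are exploratory; nominal p-values will be reported with 95% CIs".
- Section 13 describes the study as hypothesis-generating, with "controlled Type I error through multiplicity adjustment for co-primary endpoints".
- Section 15 lists the content of the ANCOVA table: baseline-adjusted mean differences with SEs and 95% CIs, p-values and partial η². No Holm-adjusted p-value is named.
- Section 16 sets the format: "exact p-values to three decimals (e.g., p=0.047). Confidence intervals at 95% two-sided".

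**The concern.** A reader who has only the overview would take each raw p-value, compare it with 0.05 and declare success on either biomarker. A reader of SAP Section 6 would require the smaller of the two p-values to be at or below 0.025 before declaring anything. One data set could then be positive under one document and negative under the other, and the Type I error control claimed in Section 13 would hold only under the SAP.

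The planned tables do not visibly close the gap. A 95% CI corresponds to a test at 0.05, so a primary interval can exclude zero when Holm does not reject. The example p-value in Section 16, 0.047, falls in the range where the two readings can part. Section 13 also uses the term co-primary, which many statisticians reserve for designs where both endpoints must succeed and no adjustment is needed. With 22 participants and no power calculation, borderline p-values are plausible, so the question is not idle.

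**Working it through.** **Inputs.** Two primary endpoints, family-wise level 0.05 and Holm (SAP Section 6); threshold 0.05 (protocol overview; SAP Section 4); 11 per arm (SAP Section 13). The documents give no effect size, SD or correlation, so those used below are assumptions.

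**The plan's own figure.** Holm with two tests compares the smaller p with 0.05/2 = 0.025 and, if that rejects, the larger p with 0.05. The bound is 0.025 + 0.025 = 0.05, which is the stated level. For independent endpoints with no true effects, it is 1 − 0.975² = 0.0494.

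**The overview read on raw p-values.** 1 − 0.95² = 0.0975 if independent, with upper bound 0.05 + 0.05 = 0.10. The verdicts differ, under no true effects, with probability 0.0975 − 0.0494 = 0.0481. By simulation with correlated endpoints:

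| Assumed correlation | Each at 0.05 | Holm | Verdicts differ |
|---|---|---|---|
| −0.3 | 0.095 | 0.048 | 0.047 |
| −0.5 | 0.091 | 0.047 | 0.044 |
| −0.8 | 0.078 | 0.040 | 0.038 |

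**With one true effect.** Assume a 0.8 SD effect on one biomarker, none on the other, baseline-to-post correlation 0.6 and independent biomarkers. The effect in residual SD units is 0.8/√(1 − 0.6²) = 1.0. ANCOVA has 22 − 3 = 19 df, and the noncentrality is 1.0 × √(11/2) = 2.35. Power is 0.605 at level 0.05 and 0.480 at 0.025. The smaller p lies between 0.025 and 0.05 with probability

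(1 − 0.480) × 0.975 − (1 − 0.605) × 0.95 = 0.507 − 0.375 = 0.132.

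Of this, (0.605 − 0.480) × 0.975 = 0.122 comes from trials in which the p-value in that window belongs to the truly affected biomarker. Most of the disagreement here is therefore power that Holm gives up, not false claims.

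**Are the two rules really different?** Holm can be written with adjusted p-values: 2 × the smaller p, and the larger of that value and the larger p. Both are compared with 0.05.

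| Raw p-values | Holm-adjusted | Raw at 0.05 | Holm |
|---|---|---|---|
| 0.047, 0.200 | 0.094, 0.200 | one positive | none |
| 0.030, 0.040 | 0.060, 0.060 | two positive | none |
| 0.020, 0.047 | 0.040, 0.047 | two positive | two positive |

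In this form the overview's threshold and Section 6 are the same rule. They differ only if the overview is taken to mean raw p-values, which it does not say.

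**Would 97.5% intervals help?** In the last row Holm rejects both endpoints, yet a 97.5% CI for the second (raw p 0.047, above 0.025) includes zero. Fixed 97.5% intervals match plain Bonferroni, so they would bring back the disagreement between interval and test that they were meant to remove.

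**The case for a change.** The best argument for a change is that the overview claims to describe the full protocol and analysis plan, states one criterion and leaves Holm out. Sections 15 and 16 do not say which p-value is printed. One sentence and one table column would prevent anyone from choosing between readings once the results are known, and would only apply the rule that the sponsor has already chosen.

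Part of this stands. The overview does omit Holm, the table specification is silent on raw versus adjusted, and the literal readings do split between 0.025 and 0.05. But the choice is not open. Section 6 names the method and the two endpoints it covers, and Section 13 relies on it. The α in Section 4 is a general default, and the specific section governs; a general 0.05 and a family-wise 0.05 do not conflict.

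The side arguments are weak. Section 13 puts co-primary next to multiplicity adjustment, which rules out the both-must-succeed meaning, so the term is merely loose. The 0.047 in Section 16 illustrates three decimals and is tied to no endpoint. A 95% CI beside a multiplicity-adjusted test is a common presentation choice and not a second decision rule.

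**Conclusion.** The concern does not hold as a defect in the plan. Followed as written, the SAP keeps the family-wise error for the two primaries at or below 0.05 (0.0494 if independent). The 9.75% arises only if Section 6 is disregarded. The disagreement rates, 4.8% with no true effects and independent endpoints and 13.2% with one assumed 0.8 SD effect, likewise describe an analysis that the SAP does not permit. The 13.2% also rests on an assumed baseline-to-post correlation of 0.6 and independent biomarkers.

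The residue is a summary paragraph that leaves out a detail and a table list that does not label its p-values. An analyst working to Section 6 has to compute the Holm result anyway, and can label raw and adjusted p-values and note that the 95% CIs are not multiplicity-adjusted. None of that alters a hypothesis, a threshold or a conclusion, so no amendment is needed.

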# 1. Administrative Information

**Trial Acronym:** SCEX-ADCRP (Stationary Combined Exercise – Adiponectin and C-Reactive Protein)

**Principal Investigator:** [name], College of Physical Education and Health, Chongqing College of International Business and Economics

**Ethics Approval:** Research Ethics Committee of Chongqing College of International Business and Economics (Approval No. K2016038; January 15, 2024)

**Study Period:** January 20, 2024 – April 10, 2024

**Study Design:** Interventional, randomized, two-arm, parallel assignment, open-label

# 2. Objectives and Endpoints

**Primary Objective:** Evaluate the effect of an 8-week high-intensity circuit-based combined exercise program on (a) serum adiponectin and (b) hs-CRP in overweight young women.

**Secondary Objectives:** Evaluate changes in body weight, BMI, body fat percentage, and VO2max.

Endpoint Class	Endpoint	Units	Time Frame
Primary	Serum adiponectin (ELISA)	µg/mL	Baseline; 48 h post-intervention
Primary	Serum hs-CRP (ELISA)	mg/dL	Baseline; 48 h post-intervention
Secondary	Body weight	kg	Baseline; 48 h post-intervention
Secondary	Body mass index (BMI)	kg/m 	Baseline; 48 h post-intervention
Secondary	Body fat percentage (BIA)	%	Baseline; 48 h post-intervention
Secondary	VO 2 max (Bruce protocol; Pollock equation)	mL·kg  ·min 	Baseline; 48 h post-intervention
Other	Correlation between Δadiponectin and Δhs-CRP	Person r (or Spearman ρ)	Change from baseline to post-intervention

# 3. Estimands and Analysis Populations

**Primary Estimand:** Mean difference between groups (Exercise vs Control) in change from baseline to 48 hours post-intervention for each primary endpoint, adjusted for baseline value.

## Analysis Populations:

**Intent-to-Treat (ITT):** All randomized participants analyzed according to assigned group.

**Per-Protocol (PP):** Subset of ITT who completed ≥ 90% of sessions (exercise arm) and had no major protocol deviations; used for sensitivity analyses.

**Safety Set:** Not applicable (behavioral intervention); adverse events during sessions will be tabulated descriptively.

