## 11. Protocol Deviations

Major deviations include missing >2 consecutive training sessions (exercise arm), receiving non-study exercise training, or violating key eligibility criteria. A deviation log will be maintained. PP analyses will exclude major deviations; ITT remains primary.

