## 12. Interim Analyses and Data Monitoring

No interim analyses or formal stopping rules were planned due to the short duration and minimal risk of the behavioral intervention.

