## **15. Tables, Listings, and Figures (TLFs)**

Pre-specified TLFs include: CONSORT flow; baseline characteristics; primary and secondary endpoint summaries (means, SDs, mean change, 95% CIs); ANCOVA results (adjusted mean differences, SEs, 95% CIs, p-values, partial  $\eta^2$ ); correlation matrix; and adverse events (counts, percentages).

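### Adverse events are tabulated for training sessions alone, so harms appearing between sessions go uncounted and the control arm yields no usable safety information

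*SAP*

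**What the plan says.** Under Analysis Populations (SAP Section 3), the safety set is "Not applicable (behavioral intervention", and "adverse events during sessions will be tabulated descriptively". No other collection window, method of ascertainment or definition of an adverse event appears in the text available.

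Two rules attach sessions to one arm. The per-protocol set requires at least 90% "of sessions (exercise arm) and had no major protocol deviations", and SAP Section 11 counts "missing >2 consecutive training sessions (exercise arm" among the major deviations. The Protocol overview says participants were "randomly assigned to either an exercise or a control group" but does not describe what the control group does.

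SAP Section 15 lists a table of "adverse events (counts, percentages", without saying which period, arm or denominator applies. SAP Section 12 gives the "minimal risk of the behavioral intervention", together with the short duration, as its reason for planning no interim analyses or formal stopping rules.

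**The concern.** The collection rule is narrower than the exposure. A strain or other training injury may first be noticed hours or days after a session. Under the stated rule it does not enter the table.

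The same injury could still leave a trace elsewhere. If it makes a participant miss three sessions in a row, it is logged as a major deviation and she leaves the per-protocol set. The trial would then record a harm only as non-adherence.

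The second problem is the control arm. If control participants attend no sessions, nobody is looking for events in them. A zero printed for control would mean no observation, yet a reader could take it as no harm. The unspecified denominator in Section 15 makes that misreading easier.

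What is at stake is the reporting of harms. The efficacy estimates do not depend on it.

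**Working it through.** The documents give no adverse-event rate or safety sample size, so there is no planned figure to reproduce. The point rests on the wording; the arithmetic shows scale.

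**Inputs from the documents**
- Schedule: an "eight-week circuit-based combined training program performed four times per week" (Protocol overview).
- Allocation: 22 participants, 11 per arm (SAP Section 13).
- Final assessment: 48 hours after the intervention (SAP Section 2).

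**Assumed inputs, not in the documents**
- Session length of 30 to 90 minutes.
- Background risk of any adverse event over the study of 5%, 10% or 20% per person.

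**1. Sessions observed by arm**
- Exercise: 8 × 4 = 32 per participant; 11 × 32 = 352 in total if all are attended.
- Control: 11 × 0 = 0, if sessions belong to the exercise arm alone.

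**2. Share of time covered**

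The span is 8 × 7 + 2 = 58 days, or 58 × 24 = 1,392 hours.

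| Assumed session length | Hours in sessions | Share of 1,392 h |
|---|---|---|
| 30 min | 16 | 1.1% |
| 60 min | 32 | 2.3% |
| 90 min | 48 | 3.4% |

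This is a share of clock time. It is not the share of harms missed, because training injuries cluster in and soon after sessions. The documents give no basis for estimating the latter.

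**3. What full collection could show in control**

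Probability of at least one affected participant among 11 = 1 − (1 − p)^11.
- p = 0.05: 1 − 0.95^11 = 43%
- p = 0.10: 1 − 0.90^11 = 69%
- p = 0.20: 1 − 0.80^11 = 91%

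Under the session-only rule the control count would be 0 at any of these risks.

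**4. What a zero is worth**

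If 11 controls were genuinely followed and none had an event, the exact two-sided 95% upper limit for the risk would be 1 − 0.025^(1/11) = 28.5%. That is weak information, but it is information. A zero from unobserved participants sets no limit at all, and the two would look identical in print.

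**5. Background events falling inside sessions**

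Take 60-minute sessions and a constant event rate over time. The chance that at least one of 11 exercisers has a background event during a session is 1 − (1 − p)^(11 × 32/1,392).
- p = 0.05: 1.3%
- p = 0.10: 2.6%
- p = 0.20: 5.5%

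So few background events would be wrongly blamed on exercise under the current wording. The main losses are delayed training harms and the absence of a control reference.

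**The case against.** The strongest reply is that a descriptive tally of events during exercise sessions is a coherent, limited output. Safety is neither an objective nor an endpoint, the trial is described as hypothesis-generating, and there are 11 participants per arm. Several stronger readings that a reader might draw go beyond the documents:

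- **That the plan commits to comparing exercise with a built-in zero.** It does not. Neither Section 3 nor Section 15 promises a table by arm or a comparison between arms.
- **That control events are zero with certainty.** This is inferred from the two rules tying sessions to the exercise arm. Control activities are not described. If control participants had supervised contacts, or if sessions included the fitness tests done in both arms, some control events could be captured. The SAP's own use of the word points to training sessions.
- **That percentages have no possible denominator.** The intention-to-treat set could supply one. The gap is that the SAP does not say which denominator applies.
- **That background events in exercisers will be widely misread as exercise harms.** Step 5 above shows this risk is small if only session events count.

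It is also fair to say that the minimal-risk statement justifies the absence of interim analyses and is not a hypothesis for the adverse-event table to test.

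What remains is the rule itself. Section 15 is worded without restriction, but a table title does not widen what is collected. Followed as written, the plan misses between-session harms and gives no usable control information.

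**Conclusion.** The point holds as a flaw in a stated rule for recording harms. Session-only tabulation covers a few percent of follow-up time at most on the assumed session lengths, and it observes 352 planned sessions in one arm against none in the other. A control zero, if shown, would be uninformative.

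This rests on three readings: that sessions means training sessions, that control participants attend none, and that no part of the SAP unavailable here sets a wider window. The 43%, 69% and 91% figures depend on assumed risks and only illustrate scale; the conclusion does not need them.

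The documents do not support a claim that the planned table is a biased comparison, because no comparison is planned. No efficacy conclusion changes. The correction is still worth making because it is cheap.

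**What to change.** Replace the safety wording in SAP Section 3 with text such as:

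> *Adverse events will be collected in both arms from randomisation to the 48-hour post-intervention visit. The same standard question will be asked of both arms at that visit. Events will be tabulated by assigned arm, with all randomised participants as the denominator. Events observed during training sessions will be shown as a separate subset.*

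Align the Section 15 entry with this window, arm structure and denominator. The in-session subset should stay separate because exercise participants can be observed at up to 32 sessions, whereas the only contacts documented for control are the two assessments. The common question gives a like-for-like basis but does not remove that imbalance.

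The Protocol overview describes the trial in the past tense, so prospective collection may no longer be possible. In that case, label the table *exercise arm, events during sessions only*, state its denominator, show control as *not assessed* rather than 0, and draw no comparative or overall safety conclusion.

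The cost is a wording change and one question at a visit that already exists. The downsides are recall error over about eight weeks and a longer list of minor events. If collection is complete, the cost is labelling alone, but the missing information cannot be recovered by it.

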# 4. General Analysis Principles

All tests two-sided with  $\alpha = 0.05$ . Continuous variables summarized by mean $\pm$ SD (or median [IQR] if non-normal); categorical variables by counts and percentages. Assumptions checked by Shapiro-Wilk (normality) and Levene's test (homogeneity of variance). When assumptions are violated, appropriate transformations (e.g., log for hs-CRP) or non-parametric methods are used.

Effect sizes and precision will be reported: adjusted mean differences with 95% confidence intervals (CI) from ANCOVA; within-group standardized mean changes (Cohen's d); and partial  $\eta^2$  for ANCOVA.

## 5. Primary Endpoint Analyses

**Endpoints:** Change in adiponectin; change in hs-CRP (baseline to 48 h post-intervention).

**Between-group comparison:** ANCOVA with post-intervention value as the dependent variable, treatment group as fixed effect, and baseline biomarker value as covariate. Secondary covariates (age, baseline BMI) may be included in sensitivity models.

**Within-group change:** Paired t-test (or Wilcoxon signed-rank if non-normal) for descriptive purposes.

**Assumption handling:** If normality is violated, log-transform hs-CRP; if variance heterogeneity persists, use robust standard errors or non-parametric Mann–Whitney U for change scores as sensitivity.

## 6. Multiplicity Control

Two primary endpoints (adiponectin and hs-CRP) will control family-wise error at 0.05 using Holm–Bonferroni adjustment. Secondary outcomes are exploratory; nominal p-values will be reported with 95% CIs.

## 7. Secondary Endpoint Analyses

**Weight, BMI, Body Fat %, VO2max:** ANCOVA framework analogous to primary endpoints (post-intervention as dependent variable, baseline value as covariate; group as fixed effect). Within-group changes summarized with paired tests.

## 8. Correlation and Exploratory Analyses

Correlation between  $\Delta$ adiponectin and  $\Delta$ hs-CRP assessed using Pearson's  $r$  (or Spearman's  $\rho$  if non-normal). Scatterplots with regression lines may be produced. Additional exploratory associations with changes in body composition may be examined with linear models (unadjusted and adjusted for age and baseline BMI).

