## 9. Missing Data Handling

Primary analysis will be complete-case under ITT. If >5% of primary endpoint data are missing, multiple imputation by chained equations (MICE,  $m=20$ ) will be performed assuming missing at random (MAR), including baseline value, group, age, BMI, and other outcomes as predictors. Sensitivity analyses will compare complete-case and MI results. Last Observation Carried Forward (LOCF) will not be used.

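### Section 8 leaves treatment group out of the correlation between the two biomarker changes and out of the exploratory change models, so an effect of exercise on both markers can appear as a link between them

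*SAP*

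**What the plan says.** The correlation appears in three places, and none of them mentions the arms.

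- Protocol, Study Protocol Overview: "Pearson correlation for associations between biomarkers".
- SAP Section 2, endpoint table, class Other: "Correlation between Δadiponectin and Δhs-CRP".
- SAP Section 8: the correlation is to be "assessed using Pearson's $r$ (or Spearman's $\rho$ if non-normal".

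Section 8 then allows further models: "Additional exploratory associations with changes in body composition may be examined with linear models (unadjusted and adjusted for age and baseline BMI".

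Elsewhere the SAP names group when group is to enter a model. The primary ANCOVA has "treatment group as fixed effect, and baseline biomarker value as covariate" (Section 5), the secondary ANCOVAs have "baseline value as covariate; group as fixed effect" (Section 7), and the imputation model is specified as "including baseline value, group, age, BMI, and other outcomes as predictors" (Section 9). The correlation matrix listed in Section 15 adds nothing about arms.

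**The concern.** For the correlation, the plan does not say whether the coefficient is pooled over arms, computed by arm or adjusted for group. One coefficient with no mention of arm reads most naturally as pooled. For the body-composition models the adjustment set is explicit and omits group.

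Both biomarkers are primary endpoints of the same intervention. If exercise moves both, the exercise women sit at one end of both change scales and the control women at the other. A pooled coefficient then combines two things: the difference between arms, and the association among women in the same arm. Section 8 does not say which is the target. A reader could take a significant pooled r as evidence that the two changes are linked within women, when it may only restate that exercise affected both markers.

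**Working it through.** **Inputs from the documents.** 22 women, 11 per arm (SAP Section 13); two-sided alpha 0.05 (Section 4); Pearson or Spearman on change scores (Section 8). The documents give no figure for the correlation, so there is none to reproduce.

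**Assumptions not in the documents.** Normal changes with SD 1 in each arm, no dropout, within-arm correlation ρ, and exercise shifting one marker by +d SD and the other by -d SD. Shifts in the same direction would reverse the sign of the induced part.

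**Closed form.** With 1:1 allocation, the arm difference adds d²/4 to each variance and -d²/4 to the covariance:

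pooled r = (ρ - d²/4) / (1 + d²/4), which for ρ = 0 is -d² / (4 + d²).

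For example, d = 0.8 gives -0.64/4.64 = -0.14; d = 1.0 gives -1/5 = -0.20; d = 2.0 gives -4/8 = -0.50.

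**Critical values.** |r| = t/√(df + t²): 0.423 for the pooled test (20 df) and 0.433 after adjusting for group (19 df).

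**Rejection rates at nominal 5%, ρ = 0.** Simulated with at least 100,000 trials per setting for the correlations and 20,000 for the linear models. In those models, age and baseline BMI were generated as unrelated to the changes. Ranges show variation between runs.

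| Shift in both markers (SD) | Pooled r | Pooled Pearson | Pooled Spearman | Model with age and baseline BMI only | Adjusted for group |
|---|---|---|---|---|---|
| 0.5 | -0.06 | 6% | 6% | 6% | 5% |
| 0.8 | -0.14 | 9% | 10% | 9% | 5% |
| 1.0 | -0.20 | 15% | 15% | 14% | 5% |
| 1.26 | -0.28 | 26% | 27–28% | 24% | 5% |
| 1.5 | -0.36 | 41–42% | 44% | 37% | 5% |
| 2.0 | -0.50 | 75% | 79% | 70% | 5% |

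Unequal shifts matter less: 7% for 0.5 and 0.8 SD, 10% for 0.5 and 1.5 SD. A shift in one marker only leaves the rate at 5%.

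**Scale.** The SAP says "the study is powered for detecting moderate-to-large effects and intended as hypothesis-generating" (Section 13) without defining those effects. If they mean 0.5 to 0.8 SD, the pooled rate is 6% to 9%. With 11 per arm, an unadjusted two-sample t-test at two-sided 0.05 has 80% power at 1.26 SD.

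**Masking.** Pooling can also hide or reverse a real association. With ρ = +0.3 the pooled value is (0.3 - 0.25)/1.25 = +0.04 at d = 1.0 and (0.3 - 0.5625)/1.5625 = -0.17 at d = 1.5. The mean group-adjusted coefficient stays at 0.29 whatever the shift.

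**The case against.** The strongest reply has five parts.

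1. **Pooling is inferred from silence.** This stands for the correlation. The contrast with the ANCOVAs is also only supporting evidence, since a model that estimates the group effect must contain group. It does not stand for the body-composition models, whose covariates are listed.
2. **A pooled r is not an error.** If exercise shifts both markers, the correlation over all 22 women really is non-zero, and rejecting zero is correct for that quantity. This stands. The rates above are false positives only for the question of a within-arm association. The documents make no within-arm or mediation claim, so the risk is one of interpretation.
3. **The size is assumed.** This stands. Material rates need shifts of about 1 SD or more in both markers. The 1.26 SD benchmark is not the trial's own detectable shift either. The planned test is baseline-adjusted ANCOVA, which lowers it, under Holm–Bonferroni, which raises it (1.40 SD for the unadjusted t-test at alpha 0.025).
4. **Group adjustment holds 5% only with equal within-arm SDs.** This stands as a limit. With the exercise-arm SD doubled in both markers and no within-arm correlation, the adjusted Pearson test rejects about 9%. At opposite shifts of 1 control SD the rates are about 9% adjusted and 10.5% pooled. The pooled test has much the same excess with no shift at all, however, and only its coefficient is biased: at shifts of 2 control SD the mean pooled r is -0.30, against 0.00 adjusted.
5. **A shift in one marker can still matter.** This stands when ρ is not zero. It creates no spurious correlation but dilutes a real one: with ρ = 0.5 and a 2 SD shift in one marker, pooled r falls to 0.5/√2 = 0.35. That is a further reason to adjust for group.

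By-arm coefficients would also remove the ambiguity, but each would rest on 11 women.

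**Conclusion.** The concern holds. Group is missing from the stated covariates of the exploratory change models, the handling of arm in the correlation is undefined, and nothing elsewhere in the documents supplies either. Run as written, these analyses mix the arm difference into the association whenever exercise shifts both variables.

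Whether that will happen cannot be known in advance, because the documents state no direction, size or joint hypothesis for the two markers. Under the assumptions above, the distortion is small at 0.5 to 0.8 SD and becomes material from about 1.0 SD in both markers. That is the situation in which both primary endpoints are most likely to be positive, and in which the correlation is most likely to be read as meaningful.

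The consequence is confined to an endpoint classed as Other and to optional models. The primary and secondary ANCOVAs include group and are unaffected. The change is worth making because it is cheap, but it does not bear on the trial's main conclusions.

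**What to change.** In SAP Section 8:

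- Define the correlation endpoint as the partial correlation (Pearson, or Spearman where needed) of the two changes adjusted for treatment group, with a 95% CI.
- Add treatment group to the linear models relating biomarker changes to body-composition changes.
- Mark the two arms on the scatterplots.
- If the pooled coefficient is also reported, label it as descriptive and as including the between-arm difference.

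The Section 2 endpoint entry and the Section 15 correlation matrix should follow the same definition.

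The cost is SAP wording and one degree of freedom: 19 instead of 20, with the critical |r| moving from 0.423 to 0.433. With a true within-arm correlation of 0.3 and no treatment effect, power falls only from 27.9% to 26.7%. No additional data are needed.
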